3.7 Vital Signs/Physical Examination

The vital signs at each visit will be assessed by treatment group using descriptive statistics.

3.8 Clinical Laboratory Assessments

The hematology and urine analysis tests will be described with the number and percentage of subjects reporting normal and abnormal (NCS and CS) results. In addition the actual results for all hematology tests will be summarized by treatment group using descriptive statistics.

3.9 Concomitant Medications

All concomitant medications recorded on the CRF will be coded and summarized according to the generic drug names using the WHO Drug Classifications. Summary will give the number and percentage of patients in the safety population who took medications that were coded to each generic drug name, as well as the number and percentage of patients that took any medication at all.

3.10 Analysis of the Study Endpoints

3.10.1 Analysis of the Primary Endpoint

To evaluate the effectiveness of tirofiban versus eptifibatide, we look at the proportion of patients with at least one of the following endpoint measurements: death, PPM, uTVR or REPLACE-2 Major bleeding within 48 hours following PCI or hospital discharge, whichever comes first. For each pairwise comparison:

- The short tirofiban group is non-inferior to the eptifibatide group;
- The short tirofiban group is non-inferior to the long tirofiban group;
- The long tirofiban group is non-inferior to the eptifibatide group;

The following hypothesis will be tested:

$$H_0: C - T \leq -0.191$$

$$H_1: C - T > -0.191$$

To test this hypothesis, the difference ($C - T$) and its associated one-sided 97.5% confidence interval will be calculated. If the lower bound of the interval is greater than -0.191, the non-inferiority will be claimed. In order to compute the risk (proportion) difference for data with binary

response (“Yes” vs. “No”), a bivariate logistic regression will be performed for each pairwise comparison with the following specifications:

- The dependent variable will be “composite endpoint” and the independent factor will be “treatment group”;
- The risk (proportion) difference between two methods as well as its confidence interval will be estimated;
- The non-inferiority margin is 19.1%

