9.1 Study Design

A randomized, multicenter, open-label study comparing tirofiban I.V. bolus injection followed by a maintenance infusion for the duration of the PCI procedure plus a minimum of one hour and up to a maximum of two hours post-PCI versus label-dosing eptifibatide. Patients were randomized to tirofiban or eptifibatide using a 1:1 allocation ratio. After 159 patients were randomized, a 1:1:1 randomization was initiated, randomizing patients to short tirofiban, eptifibatide or long tirofiban. Randomization in the long tirofiban arm is completed, changing the allocation ratio back to 1:1. Patients are mandated to stay a minimum of 18 hours following PCI.

Physician-directed standard background therapies will include dual oral antiplatelet therapy with aspirin and an approved oral P2Y₁₂ antagonist as well as antithrombotic therapy with unfractionated heparin. Physician-directed P2Y₁₂ antagonist therapy and choice of femoral or radial access site must be pre-specified prior to randomization.

The first 159 patients were randomized to the following two treatment arms on a 1:1 basis:

1. Tirofiban (25 µg/kg bolus followed by a 0.15 µg/kg/min infusion for the duration of the PCI procedure plus a minimum of one hour and up to a maximum of two hours post-PCI).
2. Eptifibatide (180 µg/kg bolus followed by a 2.0 µg/kg/min infusion for 18 hours post-PCI [minimum 12 hours mandated], with a second 180 µg/kg bolus 10 min after the first).

The three treatment arms for enrollment after the 159th patient were:

1. Short Tirofiban (25 µg/kg bolus followed by a 0.15 µg/kg/min infusion for the duration of the PCI procedure plus a minimum of one hour and up to a maximum of two hours post-PCI).
2. Eptifibatide (180 µg/kg bolus followed by a 2.0 µg/kg/min infusion for 18 hours post-PCI [minimum 12 hours mandated], with a second 180 µg/kg bolus 10 min after the first).
3. Long Tirofiban (25 µg/kg bolus followed by a 0.15 µg/kg/min infusion for 18 hours post-PCI) [minimum 12 hours mandated].

Enrolment in the Long Tirofiban arm is completed. Enrolment continues in the Short Tirofiban and Eptifibatide arms as outlined above.

Approximately 550 patients will be enrolled into the study.

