9.2 Statistical Alternative Hypothesis (Ha)

The first primary test is that short tirofiban is non-inferior to eptifibatide for death, PPM, uTVR or REPLACE-2 Major bleeding within 48 hours following PCI or hospital discharge, whichever comes first. The original non-inferiority margin was 12.4% (with an expected pooled rate of 32.5%), but based on the higher observed pooled event rate of 51% after 159 randomized patients, the non-inferiority margin was revised to be 19.1% in order to maintain the same relative margin (i.e. $12.4\% / 32.5\% = 19.1\% / 51\% = 0.38$) For the co-primary tests, the same non-inferiority margin (19.1%) will be used.

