2.4 Study Design

This is a randomized, multicenter, open-label study comparing tirofiban I.V. bolus injection followed by a maintenance infusion for the duration of the PCI procedure plus a minimum of one hour and up to a maximum of two hours post-PCI versus label-dosing eptifibatide. Patients were randomized to tirofiban or eptifibatide using a 1:1 allocation ratio. At 159 randomized patients, a 1:1:1 randomization was initiated, randomizing patients to short tirofiban, eptifibatide or long tirofiban. Enrolment in the long tirofiban arm has been completed. Patients are mandated to stay a minimum of 18 hours following PCI.

Physician-directed standard background therapies will include dual oral antiplatelet therapy with aspirin and an approved oral P2Y12 antagonist as well as antithrombotic therapy with unfractionated heparin. Physician-directed P2Y12 antagonist therapy and choice of femoral or radial access site must be pre-specified prior to randomization.

The first 159 patients were randomized to the following two treatment arms on a 1:1 basis:

1. Tirofiban (25 µg/kg bolus followed by a 0.15 µg/kg/min infusion for the duration of the PCI procedure plus a minimum of one hour and up to a maximum of two hours post-PCI).
2. Eptifibatide (180 µg/kg bolus followed by a 2.0 µg/kg/min infusion for 18 hours post-PCI [minimum 12 hours mandated], with a second 180 µg/kg bolus 10 min after the first).

The three treatment arms for enrollment after the 159th patient were:

1. Short Tirofiban (25 µg/kg bolus followed by a 0.15 µg/kg/min infusion for the duration of the PCI procedure plus a minimum of one hour and up to a maximum of two hours post-PCI).
2. Eptifibatide (180 µg/kg bolus followed by a 2.0 µg/kg/min infusion for 18 hours post-PCI [minimum 12 hours mandated], with a second 180 µg/kg bolus 10 min after the first).
3. Long Tirofiban (25 µg/kg bolus followed by a 0.15 µg/kg/min infusion for 18 hours post-PCI) [minimum 12 hours mandated].

The short tirofiban versus eptifibatide comparison involves approximately 500 patients; the short tirofiban versus long tirofiban comparison involves approximately 350 patients; and the long tirofiban versus eptifibatide comparison involves approximately 350 patients. Approximately 550 patients will be enrolled into the study.

The study procedures to take place during the course of the study are summarized in the following Schedule of Evaluations and Procedures ([Table 1](#)).

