2.5 Study Duration

Subject enrolment in the Long Tirofiban arm has been completed. Enrolment continues in the Short Tirofiban and Eptifibatide arms as outlined in [Section 2.4](#) above.

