2.6 Sample Size

The primary outcome variable for this trial is the composite of death, PPM, uTVR or REPLACE-2 major bleeding.

Sample size calculations ensure that the one-sided non-inferiority hypothesis of the first primary outcome can be tested with a type-I error rate of 2.5% and 99% power. An event rate of 32.5% was assumed for the active control and test group, which was then later adjusted to be 51% based on pooled analysis after 159 randomized patients. A sample size re-estimation was conducted after 159 randomized patients.

For the two co-primary tests, a sample size of approximately 350 was obtained by setting the non-inferiority margin at 19.1%, power at 94.5% and a 1-sided alpha at 0.025 assuming an event rate of 51%.

For the secondary endpoints involving ≥ 10 times troponin and comparing short tirofiban to eptifibatide, a sample size of approximately 500 was obtained by setting the noninferiority margin at 12.4%, power at 85% and a 1-sided alpha at 0.025 assuming an event rate of 32% (based on ≥ 10 times troponin elevation data from the 159 randomized patients).

SAS version 9.2 (SAS Institute, Cary, NC) was used for the sample-size calculations.

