2.9.1.3 Definition of Composite Endpoint

- Death due to any cause will be assessed through to 48 hours following PCI or hospital discharge, whichever comes first.
- Periprocedural myonecrosis will have occurred if there is at least one troponin (troponin I or troponin T) value of ≥ 3 times the upper limit of normal and at least 20% or greater than the baseline troponin value, per the troponin Local Laboratory, within 48 hours following PCI or hospital discharge, whichever comes first.
 - To be included in the primary composite endpoint analysis and in the secondary PPM endpoint analysis, a patient must have the pre-PCI troponin Local Laboratory measurement and at least one troponin Local Laboratory measurement within 48 hours following PCI or hospital discharge, whichever comes first.

- Patients without a pre-PCI troponin Local Laboratory measurement will not be included in the PPM endpoint analysis but will still be included in the intention to treat analysis and be analyzed for death and uTVR.
 - Patients without any troponin Local Laboratory measurements within 48 hours following PCI or hospital discharge, whichever comes first will not be included in the PPM endpoint analysis but will still be included in the intention to treat analysis and be analyzed for death, uTVR and major bleeding.
- Urgent Target Vessel Revascularization (uTVR) is either a PCI following the index PCI, or any CABG procedure performed after the index PCI on a non-selective basis in the target vessel because of recurrent myocardial ischemia. A revascularization procedure in the target vessel is considered urgent if it is due to one or more episodes of chest pain, presumed to be ischemic in origin and lasting at least 5 minutes, and results in either urgent repeat PCI or urgent coronary artery bypass surgery involving the target vessel. In the absence of pain, new ischemic ST-segment or T-wave changes, acute pulmonary edema, ventricular arrhythmias presumed to be ischemic in origin will constitute sufficient evidence of ischemia. The episode of ischemia leading to urgent repeat PCI must occur following completion of the index PCI and guidewire removal. For uTVR to count towards the primary composite endpoint, uTVR will have to be initiated during the course of the study (i.e., 48 hours following PCI or hospital discharge, whichever comes first).
- Major bleeding is defined using the criteria from the REPLACE-2 trial. Major bleeding is defined as follows:

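### Both long-tirofiban co-primary tests mix concurrent and non-concurrent comparators with no term for enrolment stage, and their stated 94.5% power is not reached within about 550 patients

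*SAP*

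**What the plan says.** Allocation ran in three stages. The first 159 patients were randomised 1:1 to short tirofiban or eptifibatide. Protocol 9.1 continues: "After 159 patients were randomized, a 1:1:1 randomization was initiated, randomizing patients to short tirofiban, eptifibatide or long tirofiban". Later, "Randomization in the long tirofiban arm is completed, changing the allocation ratio back to 1:1". SAP 2.5 confirms the last stage: "Subject enrolment in the Long Tirofiban arm has been completed. Enrolment continues in the Short Tirofiban and Eptifibatide arms".

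For each of the three pairs, SAP 3.10.1 states that "a bivariate logistic regression will be performed for each pairwise comparison with the following specifications"; the only independent factor listed is treatment group. SAP 3.2 defines the mITT population as everyone randomised who had PCI and received study drug. SAP 2.9.1.3 adds a troponin condition: "To be included in the primary composite endpoint analysis and in the secondary PPM endpoint analysis, a patient must have the pre-PCI troponin" measurement and at least one afterwards. Neither section mentions enrolment stage.

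On size, SAP 2.4 says: "The short tirofiban versus eptifibatide comparison involves approximately 500 patients; the short tirofiban versus long tirofiban comparison involves approximately 350 patients". It gives about 350 for long tirofiban versus eptifibatide as well, and about 550 in total. SAP 2.6 says: "For the two co-primary tests, a sample size of approximately 350 was obtained by setting the non-inferiority margin at 19.1%, power at 94.5" per cent, one-sided alpha 0.025 and a 51% event rate.

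**The concern.** A patient enrolled before the long arm opened or after it closed could not have been assigned to it. Using such patients as comparators for long tirofiban is a non-randomised comparison across time. If the event rate outside the 1:1:1 stage differs from the rate inside it, the estimated difference moves, and randomisation gives no protection. A shift common to all arms makes one of the two long-tirofiban tests too lenient and the other too strict.

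Nothing else in the plan deals with this. Randomisation is stratified by access site only (SAP 2.8). The exploratory covariates in SAP 3.10.4 and Table 15(a) omit stage. The imbalance clause in Protocol 9.6 is discretionary and concerns patient characteristics.

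Zero drift should not be taken for granted. The composite includes a troponin criterion read in local laboratories and not adjudicated, and P2Y12 therapy is left to the physician. These are reasons for caution, not evidence that drift occurred.

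**Working it through.** **Inputs.** Margin 19.1 points, event rate 51%, one-sided alpha 0.025, 350 per pair, power 94.5% (SAP 2.6). Pair totals 500/350/350 and overall total 550 (SAP 2.4). 159 patients before the 1:1:1 stage, about 79.5 per arm. The size of the long arm, L, is not stated. All drift values are assumptions.

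**1. The plan's own figure.** Power = Φ(0.191/SE − 1.96), with SE = √[0.51 × 0.49 × (1/n₁ + 1/n₂)]. At 175:175, SE = 0.0534 and power = Φ(3.574 − 1.96) = 94.7%. The sample size for 94.5% comes out at 348. So 350 and 94.5% reproduce, for two equal arms of 175.

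**2. What the totals imply for L.**
- Pairs of 500, 350 and 350 sum to 1,200, so the total is 600, with short = eptifibatide = 250 and L = 100.
- A total of 550 with a 500 pair gives L = 50.
- A total of 550 with two 350 pairs gives L = 150, but a 1:1:1 stage of that size needs 159 + 3 × 150 = 609 patients.
- The ceiling within 550 is (550 − 159)/3 ≈ 130. Short plus eptifibatide would then be about 420, with almost nobody enrolled after closure.

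The four totals cannot all hold.

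**3. Non-concurrent share and power.** With S patients in each comparator arm, about L of them are concurrent, so the non-concurrent share is (S − L)/S.

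| L (total) | S | Non-concurrent share | Pooled power | Concurrent-only power |
|---|---|---|---|---|
| 50 (550) | 250 | 200/250 = 80% | 69.4% | 48.0% |
| 100 (600) | 250 | 150/250 = 60% | 89.8% | 77.1% |
| 100 (550) | 225 | 125/225 = 56% | 88.9% | 77.1% |
| 130 (550) | 210 | 80/210 = 38% | 92.8% | 86.9% |

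**4. Type I error under assumed drift.** Let n₁ and n₃ be the patients per comparator arm before and after the 1:1:1 stage, and d₁ and d₃ their shifts relative to it. The bias is (n₁d₁ + n₃d₃)/S. At a true difference of 19.1 points, the lenient test passes with probability Φ(|bias|/SE − 1.96).

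Example: short versus long, L = 100, total 600, both outer stages 10 points lower. Bias = 150 × 10/250 = 6.0 points, or 31% of the margin. SE = √(0.641 × 0.359/250 + 0.51 × 0.49/100) = 0.0585. The result is Φ(1.026 − 1.96) ≈ 17.5%.

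Normal-approximation results for the lenient test (%):

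| L (total) | Steady trend, 5 each side | Steady trend, 10 each side | First 159 only, 10 | Same direction, 5 | Same direction, 10 |
|---|---|---|---|---|---|
| 50 (550) | 3 | 4 | 6 | 8 | 18-20 |
| 100 (600) | 3 | 3 | 8 | 7-8 | 17-19 |
| 100 (550) | 3 | 4-5 | 9 | 7 | 15-16 |
| 130 (550) | 5 | 10-11 | 10-11 | 5-6 | 10-11 |

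A steady trend partly cancels because the outer stages err in opposite directions. With L = 100 and a total of 600, the bias for 10 points each side is (79.5 × 10 − 70.5 × 10)/250 = 0.36 points. At L = 130 there is almost no third stage to cancel the first.

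Simulation of the planned pooled test agrees: 1.9-2.9% with no drift; at most 3.6% or 4.5% under a steady trend at L = 50-100; about 5.5-10.5% if only the first 159 differ by 10 points; 5-8% or 10-18% for a one-direction shift of 5 or 10 points. The formula runs up to about 2 points high in the most extreme cell.

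**The case against.** The strongest objection is that drift is wholly hypothetical. The only stage-specific rate comes from Protocol 9.2, which revised the margin "based on the higher observed pooled event rate of 51% after 159 randomized patients"; no later rate is given. This stands. A reader might infer that these tests are already biased, or that 15-20% is the expected error rate. The documents support neither. Those values need a 10-point shift in the same direction both before and after the 1:1:1 stage, and an ordinary trend does much less at L = 50-100.

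The renal-dosing changes in Protocol Appendix 3 do not fill the gap. They concern only renally impaired tirofiban patients, and the second change, after patient 167, falls inside the 1:1:1 stage.

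A reader might also infer that only a concurrent analysis is acceptable. That goes too far. In simulation, a stage-adjusted model held type I error at 1.6-2.8% under drift common to all arms, with power of about 83-84% at L = 100 against 77-78% for concurrent-only (57-58% against 46-48% at L = 50). Its weakness is arm-specific drift: with short 5 points lower and eptifibatide 5 points higher outside the 1:1:1 stage, its error was 6.1-6.9%, while concurrent-only stayed near 2.5%. Nothing in the documents points to such a pattern, so the choice is a genuine trade-off.

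Finally, 94.5% power does not strictly require 175:175. A 230:150 split gives about 95%, but it needs about 609 patients.

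**Conclusion.** The structural point holds on the documents alone: both long-tirofiban co-primary tests combine randomised and non-concurrent comparators, and the model ignores enrolment stage. Between about 38% and 80% of each comparator arm is non-concurrent, depending on the unstated long-arm size. The consequence for type I error is conditional on assumed drift: none if rates were stable, modest under a steady trend unless the long arm is near its ceiling, and serious only under a large one-direction shift.

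The power shortfall needs no drift assumption. At the plan's own 51% rate and margin, no layout within about 550 patients reaches 94.5%; the best is about 93%. Short tirofiban versus eptifibatide was randomised 1:1 throughout and is unaffected. The point should be fixed before the final analysis, but it does not threaten the first primary test.

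**What to change.** For the two long-tirofiban tests only, replace the treatment-only model in SAP 3.10.1 with an analysis that accounts for enrolment stage (first 159; 1:1:1; after long-arm closure). Two forms are acceptable:
- a stage-adjusted risk difference, standardised to the 1:1:1-stage patients; or
- the same risk-difference test restricted to patients randomised in the 1:1:1 stage.

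Pre-specify which is primary. Report the other beside it and the pooled analysis as a sensitivity analysis. State that the stage-adjusted model assumes drift common to all arms. Give the actual long-arm size, reconcile the 500/350/350/550 totals, and restate power for the chosen analysis; concurrent-only would have about 48% at 50:50, 77% at 100:100 and 87% at 130:130.

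The cost is SAP wording, minor programming from the randomisation order, and some nominal power. At L = 100 the loss from the pooled 89-90% is about 6 points with the stage-adjusted model and about 12 with concurrent-only; at L = 50 it is about 12 and 21 points. Leave short tirofiban versus eptifibatide as planned.

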9.6 Planned Methods of Analysis

General Principles

For continuous variables, descriptive statistics (mean, SD, median, and quartiles) will be tabulated by treatment group. For categorical variables, the number and proportion of patients in each category will be tabulated.

The primary and secondary endpoints will be analyzed using the MITT population. Safety endpoints will be analyzed using the safety population. Demographics, baseline characteristics, and other study assessments will be analyzed using the MITT and intent-to-treat (ITT) population.

Confidence intervals will be used to assess hypotheses of non-inferiority and superiority. Details of the statistical methods will be developed in the Statistical Analysis Plan (SAP).

Demography and Baseline Characteristics

All appropriate background data will be summarized for each treatment group. If there are heterogeneities between two groups in any of the patient characteristics that are of clinical importance or could affect the study outcome, the impact of the imbalances will be investigated. If necessary, adjustments may be made in the efficacy and safety analysis and will be documented in the study report.

Primary Endpoint

The first primary and co-primary endpoints will be analyzed by the use of a one-sided 97.5% confidence interval

Subgroup/Covariate Analyses

Formal subgroup analyses will be performed by including the appropriate interaction terms in multivariable logistic regression models. The effects of potential covariates (see Section 9.3.4) will be assessed using multi-variable logistic regression.

Secondary Endpoints

The analysis of the secondary endpoints will be conducted in the same way as for the primary endpoint.

Safety Endpoints

The analysis of these safety endpoints will compare the incidence in the short tirofiban treatment group to the incidence in the eptifibatide group, the incidence in the short tirofiban treatment group to the incidence in the long tirofiban treatment group and the incidence in the long tirofiban treatment group to the incidence in the eptifibatide group, using the Fisher's mid-p (Berry and Armitage, 1995). Serious adverse events will also be tabulated overall and by severity for each treatment group.

Multiplicity (Multiple Endpoints)

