2.8 Randomization

Once all baseline examinations and tests are completed, the site will once again carefully review the inclusion and exclusion criteria described in the protocol to ensure that the patient is eligible to enter the study.

Naming of oral P2Y12 antagonist agent (clopidogrel, prasugrel, or ticagrelor) to be used post-randomization must be pre-specified prior to randomization.

Selection of either the femoral or radial access site must be pre-specified prior to randomization.

Randomization may occur only if all of the following criteria are satisfied:

- a. Consented patient is confirmed to be eligible for the study, AND
- b. name of intended oral P2Y12 antagonist agent used post-randomization is prespecified, AND
- c. access site for PCI is pre-specified, AND

- d. decision to proceed to PCI is finalized, AND
- e. timing between randomization and initiation of the PCI procedure is less than 2 hours.

Once the above criteria are satisfied, the patient may be randomized. The timing for randomization in this study is critical. The reason for timing the study drug administration so close to time of PCI is to minimize inappropriate patient enrollment. Situations where this might occur include the procedure where PCI is aborted or otherwise not performed or when a decision is made not to administer study medication for whatever reason.

At randomization, the patient will be assigned a study number that will allow identification of the patient throughout the study, and the appropriate staff will prepare the corresponding study drug. Patients will be randomized via a centralized randomization system to receive either tirofiban or eptifibatide.

The randomization will stratify patients according to femoral or radial access.

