3.10.4 Potential Covariates and/or Subgroups

As an exploratory analysis, appropriate univariate statistics will be used to identify potential confounders for inclusion in multivariable regression models for assessment of the primary endpoint. The following covariates will be considered:

- Patient with acute coronary syndromes (defined as any previous diagnosis of unstable angina, NSTEMI or STEMI)
- STEMI > 48 hours
- Stable angina
- Baseline troponin (positive vs. negative)
- Planned PCI access (femoral vs. radial)
- Number of stents implanted
- Number of vessels treated (multivessel vs. single vessel)
- Total infusion time
- Patients receiving P2Y12 antagonist therapy between 24 and 6 hours prior to randomization
- Patients receiving P2Y12 antagonist therapy between 6 and 1 hours prior to randomization
- Patients receiving P2Y12 antagonist therapy between 1 hour prior to randomization and 15 minutes after completion of the PCI procedure
- Type 2 diabetes mellitus
- Age < 65 years, ≥ 65-74 years and ≥ 75 years
- Sex
- Clopidogrel
- Prasugrel
- Ticagrelor
- Indication for PCI (Urgent vs. Elective)

RESPONSIVE
RELIABLE
RESULTS

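### Randomisation is stratified by femoral or radial access, but the model that decides all three non-inferiority tests contains treatment only: a small loss of precision that one SAP sentence would recover

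*SAP*

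**What the plan says.** **Randomisation.** SAP 2.8, matching Protocol 5.2.2, states: "The randomization will stratify patients according to femoral or radial access". No other stratification factor is named. The same section fixes the factor at baseline: "Selection of either the femoral or radial access site must be pre-specified prior to randomization".

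**Primary analysis.** Protocol 9.6 says only this: "The first primary and co-primary endpoints will be analyzed by the use of a one-sided 97.5% confidence interval". It names no strata and leaves the detail to the SAP. SAP 3.10.1 supplies it: "a bivariate logistic regression will be performed for each pairwise comparison". The dependent variable is the composite and the only independent factor is treatment group. The risk difference, control minus test, and its interval come from that model. The rule is: "If the lower bound of the interval is greater than -0.191, the non-inferiority will be claimed". SAP 3.10.2 gives the secondary endpoints the same analysis.

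**Where access does appear.** SAP 3.10.4 opens: "As an exploratory analysis, appropriate univariate statistics will be used to identify potential confounders". Planned access is one of the 18 candidates that follow. Mock Table 15(a) repeats the list and Table 13 tabulates planned access by arm. No provision keeps access in any model.

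**The concern.** A stratified randomisation is normally analysed with its strata. If the factor predicts outcome and allocation is balanced within strata, the between-stratum part of the outcome variance does not contribute to the error of the treatment comparison. A treatment-only model still counts that part, so its interval is wider than the design warrants.

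The second issue is balance. Randomisation balances access among those randomised, but the primary analysis uses fewer patients. It requires PCI and study drug (SAP 3.2), a pre-PCI troponin and at least one post-PCI troponin (SAP 2.9.1.3), and nothing is imputed (SAP 3.13). If those exclusions shift the access mix between arms, the deciding estimate has no means of correcting for it.

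Access could plausibly be prognostic: sheath puncture is a listed bleeding site (Protocol 7.1.1), and overt blood loss with a sufficient haemoglobin drop is major bleeding, a component of the composite. Neither document says how strong the relation is.

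**Working it through.** **Inputs from the documents.** Event rate 51% in both arms, margin 19.1 points, one-sided alpha 0.025. First primary test: about 500 patients, 99% power. Co-primary tests: about 350 patients, 94.5% power.

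**Inputs assumed.** Radial share 20% to 50%; femoral-radial gap in the composite rate 0 to 20 points; allocation balanced within strata.

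**1. The plan's own sample sizes.** With n per arm = (z₁₋α + z_power)² × 2p(1−p) / margin²:
- First test: (1.960 + 2.326)² × 2 × 0.2499 / 0.191² gives 252 per arm, 504 in total, against about 500 stated. Power at 500 is 98.96%.
- Co-primary tests at 1:1: 348 in total, against about 350 stated.

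The stated figures therefore follow from an unstratified two-proportion formula.

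**2. Unadjusted half-width at 250:250.** 1.96 × √(0.2499 × (1/250 + 1/250)) = 1.96 × 0.0447 = 8.76 points.

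**3. Stratified half-width.** With radial share w and gap d, the within-stratum variance is p(1−p) − w(1−w)d². For w = 0.5:
- d = 0.10: 0.2499 − 0.0025 = 0.2474; half-width 1.96 × √(0.2474 × 0.008) = 8.72 points.
- d = 0.20: 0.2499 − 0.0100 = 0.2399; half-width 1.96 × √(0.2399 × 0.008) = 8.59 points.

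**4. Type I error of the unadjusted bound.** 1 − Φ(1.96 × SE_unadjusted / SE_stratified). For w = 0.5 and d = 0.20 the ratio is 1/0.9798, giving 0.0227.

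Ranges over a radial share of 20% to 50%, at 250:250:

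| Assumed gap (points) | Stratified half-width | Narrowing | Type I error, unadjusted | Power, unadjusted | Power, stratified |
|---|---|---|---|---|---|
| 0 | 8.76 | 0 | 0.0250 | 98.96% | 98.96% |
| 5 | 8.75–8.76 | 0.01 | 0.0249 | 98.97% | 98.97–98.98% |
| 10 | 8.72–8.74 | 0.03–0.04 | 0.0244–0.0246 | 98.98–98.99% | 99.00–99.02% |
| 20 | 8.59–8.65 | 0.11–0.18 | 0.0227–0.0235 | 99.04–99.08% | 99.10–99.18% |

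Simulation (200,000 trials per scenario, radial share 30% to 50%) agrees. Type I error of the unadjusted bound was 0.0244–0.0246 with no access effect and 0.022–0.023 at a 20-point gap. With stratification it was 0.024–0.025 throughout.

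**5. Long-tirofiban comparisons.** Comparison sizes of 500, 350 and 350 solve to arms of 250, 250 and 100. These sum to 600 against about 550 stated, so the split is only indicative. At 250:100 and a 20-point gap the half-width goes from 11.59 to 11.36–11.44 points, and power from about 90.1–90.2% to 90.5–90.9%. That is a gain of 0.4 to 0.7 points, still small.

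**6. Imbalance in the analysed set.** A difference in radial share between arms shifts the unadjusted risk difference by that difference times the gap. As an assumed illustration, a 5-point difference in share with a 10- to 20-point gap gives 0.05 × 0.10 = 0.5 to 0.05 × 0.20 = 1.0 points, in either direction. The documents do not show that such an imbalance exists.

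**The case against.** **The error is on the safe side.** This stands. Non-inferiority needs the bound to clear −0.191, so an interval that is too wide cannot manufacture a claim. A reader might infer that omitting the strata makes the deciding test invalid or liberal. With balance within strata, the calculated type I error is never above 0.025.

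**The gain is tiny.** This stands too. One event in an arm of 250 moves its rate by 0.4 points, more than twice the largest narrowing in the table.

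**Access-site bleeding cannot carry the argument.** Largely right. In the abbreviated-eptifibatide trial cited in Protocol 1.3, major bleeding was 1.0% and 4.2%. Take 4.2% overall, a 50:50 access split and every bleed in femoral patients: the bleeding gap is 8.4 points, or 0.25 × 0.084² / 0.2499 = 0.7% of outcome variance. If components are independent, about half those bleeds fall in patients who already have another component event. The composite gap is then about 4.2 points, or 0.18%. A larger gap would need access to predict troponin release, on which the documents are silent. Nor should a reader infer a consequence for the primary safety endpoint: SAP 3.10.3 tests it by Fisher's mid-p, which this change leaves alone.

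**Imbalance is already provided for.** Only partly. Protocol 9.6 promises to investigate baseline imbalances and allows adjustment if necessary, Table 13 would show an access imbalance, and Table 15(a) could adjust for it. All of this is discretionary or exploratory, and none of it alters the bound in SAP 3.10.1.

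**The width argument is conditional.** It requires balance enforced within strata, and neither document describes the allocation method beyond saying that it is stratified.

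**Conclusion.** The mismatch is real: the trial randomises by planned access and decides all three non-inferiority tests on a model without it. The severity is minor. If allocation is balanced within strata, the planned bound is valid and slightly conservative. For assumed gaps of 0 to 20 points and a radial share of 20% to 50%, the cost at 250:250 is 0 to about 0.2 points of half-width and less than 0.3 points of power. The documents give neither the gap nor the share, and a gap near zero, with no gain at all, is quite possible.

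The documents do not support reading this as a threat to the non-inferiority conclusion. The case for change is that the analysis should follow the randomisation, and that the treatment of access should be fixed in advance in an open-label trial whose endpoints are not adjudicated. A pre-specified stratified estimate would also correct for any access imbalance in the analysed set.

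**What to change.** In SAP 3.10.1, pre-specify each pairwise risk difference stratified by planned access as randomised, not by access actually used. Mantel-Haenszel weights with a stratified Miettinen-Nurminen or Newcombe interval would serve; so would standardised risks from a logistic model with treatment and access. Take the one-sided 97.5% bound from that estimate, leave the margin and decision rule unchanged, and report the treatment-only result as a sensitivity analysis.

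In SAP 3.10.2, apply the same method to the composite and troponin-based secondary endpoints. Sparse endpoints such as 48-hour death and uTVR may stay unstratified. Mock Tables 15 and 17 need matching labels and a row for the sensitivity result.

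The cost is a sentence or two in the SAP and a few lines of code, settled before the data are analysed. It needs no new data and no change in sample size, because planned access is already required before randomisation.
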